Under a HIPAA waiver, a list of all potential candidates will be generated from the Joslin Electronic Medical Records every three months. Candidates will be sent a letter explaining the study in simple terms, including a phone number to call in order to "opt-out". The letter may be mailed or given to the patient at the time of a clinic visit by clinic personnel. If the potential research subject does not decline further contact in two weeks, the study staff will invite him/her to participate in the study by telephone or at the time of their next visit. Prospective study subjects may also be informed of the study by their Joslin clinicians, who may provide them with information on how to contact study coordinators. Patients who agree to participate will be screened by telephone or in person to determine eligibility. Subjects who meet screening criteria will be mailed or given an informed consent form and will be invited to come to the Joslin CRC for the study visit. Written consent will be obtained after explaining again the purpose and procedures of the study. In the initial contact and

again at the time of the screening visit, study subjects will be encouraged to ask questions and they will be reassured that they may withdraw from the study at any time without impact on clinical care.

Participants will also be recruited via Research Match, a secure online recruitment tool. Research Match allows for recruitment searches for individuals who have registered on their site and are interested in being contacted with research opportunities. An informational email about the study is then sent out through the Research Match portal to the potential participants whose information is de-identified in the initial search. For those who respond to the initial email that they are interested (by clicking within the message), their contact email will be sent to the study specific Research Match portal (password protected), and the study team will respond to each person individually with a follow-up email to schedule phone screening. For those that are not interested, they are able to click "not interested" and opt out of further communications, or not respond at all to the initial recruitment email.

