The hypoglycemia patient population is highly motivated by the frustration of this disease; we anticipate no difficulty in recruitment or retention for this population. As involvement will include initial telephone or in-person screening and a single study visit with history and testing, we do not anticipate significant attrition in this protocol. Our study team has extensive experience with recruitment and retention of post-bariatric patients in the context of the SLIMM-T2D and ARMMS-T2D longitudinal clinical trial, and in prior studies of post-bariatric hypoglycemia.

b. Inclusion and Exclusion Criteria

Initial general screening will be performed during an initial phone or in person visit (e.g. during a clinical visit), which will include administration of the Patient Health Questionnaire-2 (PHQ-2).

Individuals who appear to meet criteria will be invited for the study visit, when a detailed history will be performed by study clinicians. Inclusion and exclusion criteria will be reviewed after the visit to determine study eligibility.

Inclusion criteria:

1. For PBH group: Males or females diagnosed with ongoing post-bariatric hypoglycemia with prior episodes of neuroglycopenia, unresponsive to dietary intervention (low glycemic index, controlled carbohydrate portions).
2. For post-RYGB without hypoglycemia: Males or females with history of RYGB and no history of symptomatic hypoglycemia.
3. For hypoglycemia without a history of upper gastrointestinal surgery group: Males or females diagnosed with ongoing hypoglycemia with prior episodes of neuroglycopenia, and without a history of prediabetes or diabetes
4. For non-surgical controls only: Males or females with no history of upper gastrointestinal surgery and no history of hypoglycemia, prediabetes, or diabetes.
5. Age 18-70 years of age, inclusive, at screening.
6. Willingness to provide informed consent and attend one study visit.

Exclusion criteria:

1. Active treatment with any diabetes medications, except for acarbose.
2. History of cerebrovascular accident.
3. History of a traumatic brain injury not related to hypoglycemia.
4. A score of 6 on the PHQ-2.

CHS Protocol Number	00000098		
Protocol Version	4.0	Version Date	5/18/2021

5. Active alcohol abuse or substance abuse.
6. Known insulinoma, gastrinoma or other neuroendocrine tumor.
7. Having undergone same / similar cognitive assessments within the last calendar year.

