There will be no involvement of special vulnerable populations such as fetuses, neonates, pregnant women, children, prisoners, institutionalized or incarcerated individuals, or others who may be considered vulnerable populations.

Please note that duration of hypoglycemia will not be included in either inclusion or exclusion criteria, but will be included as a covariate in our analyses.

c. Number of Subjects

Participants will be recruited into 4 groups, (1) patients with PBH, recruited from the Joslin Hypoglycemia Clinic, (2) asymptomatic post-RYGB patients, recruited by advertisement flyers at postoperative surgical clinics at local hospitals (e.g. Brigham and Women's and Beth Israel Deaconess Hospitals), (3) patients with hypoglycemia and no history of upper gastrointestinal surgery, and NO current diagnosis of diabetes or pre-diabetes, recruited from the Joslin Hypoglycemia Clinic, (4) controls, recruited by local advertisement. We anticipate screen failure and drop out rate of 20% each. We plan to enroll patients with hypoglycemia continuously over the next 4 years. We anticipate performing cognitive testing in up to 20 participants in each of the four groups, based on availability of grant funding.

d. Study Timelines

The total duration of the study will be one to three weeks: one screening call and one study visit. We anticipate recruitment to continue for up to 4 years, concurrent with grant funding.

There is no plan in the current study to re-contact patients after the study has been completed.

e. Study Endpoints

Primary endpoints:

- Assessment of memory

Secondary endpoints:

- Assessment of executive function, language and psychomotor speed
- Assessment of depressive symptoms using the Beck Depression Inventory (BDI)
Analysis to assess the effects of participant group, and BDI scores (depressive symptoms), on standardized quantitative scores for each cognitive domain assessed (memory, executive function, language and psychomotor speed).

f. Study Procedures

An initial pre-screening phone call will occur with focus on inclusion, and exclusion criteria. The PHQ-2 will be administered as part of the screening process to assess for the presence, on a nearly daily basis, of both of the two cardinal symptoms of major depressive disorder. Individuals will be told that as part of the screening process they will be asked 2 questions about symptoms related to their mood. For individuals who

CHS Protocol Number	00000098		

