Protocol Version	4.0	Version Date	5/18/2021

are ineligible due to their PHQ-2 score, the study physician or nurse practitioner will offer to contact their primary care physician and recommend referral for mental health assessment. PHQ-2 forms completed via phone for those who are not eligible or who do not want to participate will be disposed of in a secure waste bin (for shredding) immediately after screening.

The study visit will then be scheduled for eligible participants. At this visit, we will test the hypothesis that hypoglycemia is associated with changes in cognitive function in the domains of memory, language, executive function, and psychomotor speed. Secondarily, we will also test the hypothesis that recurrent hypoglycemia is associate with higher scores on the BDI (depressive symptoms), and that BDI scores will be negatively correlated with cognitive function.

Sites: Participants will be recruited at Joslin Diabetes Center and via advertisement. All clinical evaluation will be performed on the clinical research unit of the Joslin Diabetes Center.

Study Visit: After informed consent, patients will undergo a history, and EKG, with emphasis on inclusion/exclusion criteria. Blood glucose will be assessed by capillary glucose. Prior to cognitive testing, participants will also be asked to complete the BDI, measuring depressive symptoms. Participants will be offered breaks of up to 10 minutes between components of the assessment.

Cognitive Testing: Prior to cognitive assessment, blood glucose levels will be assessed by capillary glucose testing. If glucose level is less than 70 mg/dL, glucose tablets and a snack will be provided, and glucose levels will be rechecked every 15 minutes until levels exceed 80 mg/dL. If during the course of testing a patient develops symptoms of hypoglycemia, blood glucose levels will be checked, and if needed, treated as above. Testing will not be resumed until glucose levels exceed 80 mg/dl.

The neuropsychological tests include:

a) Intelligence

The National Adult Reading Test (NART) is composed of a list of 50 words that progress in level of difficulty. The participant is instructed to read each word aloud while the examiner tracks the number of errors made. This test was designed in order to estimate premorbid intelligence based on the test taker's word familiarity.

b) Working Memory and Attention

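### Final eligibility is decided after the only study visit, and so after the depression score and all cognitive outcomes are collected, with no masking stated

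*Combined protocol and SAP*

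**What the plan says.** Section III.b describes an initial phone or in-person screen, followed by the visit: "Individuals who appear to meet criteria will be invited for the study visit, when a detailed history will be performed by study clinicians". The next sentence reads "Inclusion and exclusion criteria will be reviewed after the visit to determine study eligibility". In context, the visit meant is the study visit.

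There is only one such visit. Section III.a speaks of "a single study visit with history and testing", and section III.d of "one screening call and one study visit".

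Section III.f sets out what happens at it: "After informed consent, patients will undergo a history, and EKG, with emphasis on inclusion/exclusion criteria". The BDI comes next, and then the cognitive battery. Memory is the primary endpoint (section III.e). The other cognitive domains and the BDI are secondary.

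Other sections place the eligibility decision elsewhere:

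- Section III.a: "Patients who agree to participate will be screened by telephone or in person to determine eligibility".
- Section III.f: "The study visit will then be scheduled for eligible participants".
- Section IX has eligibility determined at a medical and screening visit after consent is signed.

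Section III.k keeps data gathered before a withdrawal unless the participant asks for removal, and lists a newly diagnosed exclusionary condition among the reasons for withdrawal.

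**The concern.** When the last eligibility decision follows the outcome measurements and the decision-maker may see them, an exclusion can depend on the result. Most criteria here are factual: age, diabetes medication, stroke, known tumor, recent cognitive testing. Several are not. Prior neuroglycopenia, failure of dietary measures, absence of symptomatic hypoglycemia in the gastric bypass comparator, whether a brain injury was related to hypoglycemia, and active substance abuse all call for judgement. The first three also determine which group a person belongs to, so a late decision on them bears directly on the comparison being made.

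The protocol's own background section lists memory impairment and changes in thinking among neuroglycopenic symptoms. A poor or good test result could therefore colour a later reading of the history.

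Reporting also suffers. A reader of the results could not tell which exclusions came before testing, or whether people excluded afterwards contributed data.

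**Working it through.** **Order of events.** The plan gives no figure to reproduce, so the first check is the sequence.

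| Step | Source | Eligibility decided here? |
|---|---|---|
| Phone or in-person screen, including PHQ-2 | III.a, III.b, III.f | Provisionally: III.b invites those who seem to qualify |
| Consent, history, EKG | III.f | Information collected; III.f records no decision |
| BDI (secondary endpoint) | III.f | No |
| Cognitive battery (primary and secondary endpoints) | III.f | No |
| Review of criteria after the visit | III.b | Yes, stated as the determination |

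Section IX's reference to screening visits does not open a separate slot before testing, because sections III.a and III.d allow one visit only. No section masks the eligibility reviewer to the scores.

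**Scale of a possible effect (illustration).** The inputs are:

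- From the plan (section III.c): "We anticipate performing cognitive testing in up to 20 participants in each of the four groups". I take 20 per group.
- Assumed, not in the documents: standard normal scores; no true group difference; in one group, the k people most extreme on an exclusion index are dropped; that index correlates rho with score; comparison with an unaffected group of 20 by two-sided t-test at 0.05.

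The expected shift in the affected group's mean is rho × (mean index of those kept). With 20 tested, the mean index of those kept is 0.098 SD for k = 1 and 0.182 SD for k = 2.

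- k = 1: 0.3 × 0.098 = 0.029; 0.5 × 0.098 = 0.049.
- k = 2: 0.3 × 0.182 = 0.055; 0.5 × 0.182 = 0.091.

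Simulation with 200,000 replicates per setting gives:

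| k dropped of 20 | rho | Mean shift (SD) | Type I error |
|---|---|---|---|
| 1 | 0 | 0 | 5.0% |
| 1 | 0.1 | 0.009 | 5.0% |
| 1 | 0.3 | 0.030 | 5.2% |
| 1 | 0.5 | 0.050 | 5.4% |
| 2 | 0 | 0 | 5.1% |
| 2 | 0.1 | 0.018 | 5.0% |
| 2 | 0.3 | 0.054 | 5.4% |
| 2 | 0.5 | 0.091 | 6.1% |

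The 5.1% at rho = 0 is simulation noise around 5%. For the planned four-group ANOVA with one group affected and k = 2, the error is 5.3% at rho 0.3 and 5.8% at rho 0.5. Reversing the direction of selection for k = 2 gives shifts of -0.054 and -0.091 SD with errors of 5.4% and 6.2%, so the bias can go either way.

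**For comparison.** Two groups of 20, two-sided 5% t-test, 80% power: the detectable difference is 0.909 SD. The largest shift above is 0.091 / 0.909 = 10% of that.

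**Extreme bound, not relied on.** If exclusions fell entirely on the lowest scorers of one group, leaving 20, one exclusion would shift the mean by about 0.09 SD (error 6.6%) and two by about 0.17 SD (9.7%). Nothing in the documents suggests selection this strong.

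**The case against.** The strongest reply is that this is one loose phrase. Everything else reads as ordinary two-stage screening: a provisional screen, then a history and EKG aimed at the criteria and listed ahead of the BDI and tests. The sentence before the disputed one speaks only of the history, so the authors may have meant after the history. Participants in the two hypoglycemia groups must already carry a diagnosis and are drawn from a specialist clinic, which narrows the room for discretion. Section III.k would keep the data of anyone withdrawn, which removes the bias if it is applied. This is also a pilot sized on feasibility, and the illustrated effects are small.

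Much of this stands. Screening does come first, most criteria are factual, the effect is probably small, and the documents show an opportunity for bias, not bias itself.

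It does not remove the point. Section III.b states a rule, and the single visit gives that rule a definite meaning. No section says that a decision is made or recorded after the history and EKG. Section III.k deals with withdrawals and does not clearly reach someone found never to have qualified. The passages on timing conflict whichever was intended.

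**Conclusion.** The concern holds. Read as written, the plan makes the final eligibility decision after every outcome has been collected, without masking, and this conflicts with sections III.a, III.f and IX.

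The statistical consequence cannot be derived from the documents and is probably small: about 0.03 to 0.09 SD, and a pairwise error of 5.2% to 6.1%. That assumes one or two score-related exclusions in one group of 20 at correlations of 0.3 to 0.5, and both the counts and the correlations are assumptions. At a correlation of 0.1 the effect is negligible. It is nil if exclusions are unrelated to score or if the data are retained.

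This should be corrected because the correction is cheap and makes the exclusions interpretable. It does not undermine the study. Confidence is medium, since the authors may have intended the decision to precede testing.

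**What to change.** Replace the sentence in section III.b with wording such as: Eligibility and group assignment will be confirmed and recorded from the screening call, history and EKG, before the BDI and cognitive tests. Any exclusion made on facts found later will be logged with its reason and decided without reference to the scores.

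Bring sections III.a, III.f and IX into line, so that the phone or in-person screen is described as provisional and the confirmation after the history and EKG as final.

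It would also help to state in section III.k whether data from people found ineligible after testing are analyzed. If any are excluded, report one sensitivity analysis that includes them, leaving out those who asked for their data to be removed.

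The cost is one sign-off during the visit, since section III.f already lists the history and EKG first, plus a short log. The extra analysis arises only if late exclusions occur. No criterion, test or sample size changes.

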CHS Protocol Number	00000098		
Protocol Version	4.0	Version Date	5/18/2021

Principal Investigator	[name].		
Study Title	Pilot Study – Cognition in Patients with Hypoglycemia, without Diabetes		

I. Objectives

The goal of this study is to evaluate the effect of recurrent hypoglycemia on cognitive function in patients who do not have diabetes. This pilot aims to identify the cognitive domains of interest, as well as inform the development of a future battery of assessments, which could be replicated in a larger sample. Ultimately, this information may have important implications for assessment of risk, patient teaching methods, and treatment, to help avoid potential cognitive decline. We will test the hypotheses that (1) recurrent hypoglycemia in patients without diabetes is associated with impairment in cognition, and (2) patients with a history of post-bariatric hypoglycemia (PBH) have impaired performance on cognitive tests as compared with patients without known hypoglycemia.

II. Background

Hypoglycemia in the absence of diabetes is generally classified in relation to its timing, and can manifest in the fasting state, with exercise, or most commonly, after meals (reactive hypoglycemia). Some patients present with predominantly one type, while others may present with mixed patterns. While there are conditions which have been identified that cause, or contribute to hypoglycemia, diagnosis can be challenging, and for some the precise etiology of hypoglycemia remains unknown.

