Despite the heterogeneity of this population, hypoglycemia yields similar symptoms and may result in some common long-term outcomes. When hypoglycemia is severe it causes not only distressing adrenergic and cholinergic symptoms, but also neuroglycopenia, with symptoms including changes in thinking, memory impairment, brain fog, headaches, and difficulty concentrating or maintaining attention. When recurrent, hypoglycemia unawareness can develop, impairing safety and increasing risk for disability, syncope, arrhythmias, seizures, coma, and death. Patients often report multiple episodes with alteration in, or loss of consciousness. Impaired cognition during acute hypoglycemia may result in inability to self-treat, thus, requiring assistance from others to both procure and administer treatment. Moreover, many individuals with recurrent hypoglycemia are disabled due to inability to perform job-related tasks, or endorse difficulty in meeting the cognitive demands of their profession, or activities of daily life.

Hypoglycemia has been extensively studied in the population of patients with diabetes; however, there is a paucity of literature describing cognition in patients with hypoglycemia, without diabetes. For patients with diabetes, hypoglycemia is induced by medications, often in combination with behavioral factors such as reduced food intake or increased activity. Hypoglycemia in the absence of diabetes can be unpredictable, even when patients are following all recommendations provided. Management of this condition can be onerous for patients. Options for therapy are limited, and medications available are not always well tolerated. Even with the best-available treatment, hypoglycemia can be a chronic, lifetime condition. Thus, the effect that this repeated neurologic insult exerts on cognition is important to understand to assess risk, improve patient teaching methods, and optimize treatment, to help avoid potential cognitive decline.

CHS Protocol Number	00000098		
Protocol Version	4.0	Version Date	5/18/2021

Preliminary Data:

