Collectively, these data highlight several important points: 1) recurrent hypoglycemia can result in unawareness, with episodes possibly more frequent than appreciated by patients, leading to clandestine damage; 2) hypoglycemia can directly result in cell damage or death, neuroinflammation, and a pro-thrombotic state; 3) hypoglycemia in patients with diabetes has been shown to have serious and detrimental cognitive consequences, both for short-term patient safety and long-term cognition; 4) it is possible that patients undergoing bariatric surgery may have a pre-existing neural vulnerability due to prior history of obesity, with subsequent hypoglycemic insults; 5) understanding the impact of recurrent hypoglycemia on cognition in this understudied group is essential for risk assessment, raising provider awareness, developing more effective patient teaching strategies, and informing treatment, to help avoid potential cognitive decline.

In this study, we will assess and compare cognitive function in patients with hypoglycemia without a history of diabetes, as well as in RYGB patients with and without PBH. We will also assess and compare depressive symptoms between groups, and their potential relationship to cognition.

III. Study Design

a. Recruitment Methods

Participants will be recruited into 4 groups: (1) patients with hypoglycemia after upper gastrointestinal surgery, recruited from the Joslin Hypoglycemia Clinic, (2) asymptomatic post-bariatric patients, recruited from postoperative surgical clinics at Brigham and Women's Hospital, (3) patients with hypoglycemia and no history of upper gastrointestinal surgery, and NO current diagnosis of diabetes or pre-diabetes, recruited from the Joslin Hypoglycemia Clinic, (4) participants without hypoglycemia or upper gastrointestinal surgery (controls), recruited by local advertisement. Some participants may be recruited from other hypoglycemia studies at Joslin.

The Joslin Hypoglycemia Clinic has emerged as a referral clinic for patients with hypoglycemia from around the country, and particularly the New England region. Over 300 individuals have been evaluated in this clinic since its inception, and new patient referrals continue to increase as the awareness of hypoglycemia is increasing among patients and physicians alike. Thus, we have immediate access to a large pool of highly motivated patients.

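### Once cognitive testing starts, glucose is rechecked only if symptoms appear, although the protocol warns of hypoglycemia unawareness; a silent low during the battery would go unrecorded and could be present at departure

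*Combined protocol and SAP*

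**What the plan says.** Section III.f (Study Visit and Cognitive Testing) requires a capillary glucose before cognitive assessment. A value below 70 mg/dL is treated with glucose tablets and a snack, then rechecked every 15 minutes until it exceeds 80 mg/dL. Once testing is under way the rule becomes: "If during the course of testing a patient develops symptoms of hypoglycemia, blood glucose levels will be checked, and if needed, treated as above". Testing that has been interrupted may resume only above 80 mg/dL. Breaks of up to 10 minutes are offered between components, with no glucose check attached. The capillary glucose listed with the history and EKG has no stated time, but it appears before the BDI and the tests.

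The Background (II) says: "When recurrent, hypoglycemia unawareness can develop, impairing safety and increasing risk for disability, syncope, arrhythmias, seizures, coma, and death". Its closing summary adds that "recurrent hypoglycemia can result in unawareness, with episodes possibly more frequent than appreciated by patients". It also says: "Impaired cognition during acute hypoglycemia may result in inability to self-treat".

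Under III.b, Group 1 (post-bariatric hypoglycemia) and Group 3 (hypoglycemia without upper gastrointestinal surgery) must have ongoing hypoglycemia with past neuroglycopenic episodes. Group 1 must also have failed dietary treatment. Unawareness is not an exclusion. Group 2 is "Males or females with history of RYGB and no history of symptomatic hypoglycemia". Section III.c plans "up to 20 participants in each of the four groups". Memory is the primary endpoint (III.e), compared across groups by ANOVA (III.h).

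**The concern.** The in-test safeguard depends on symptoms, and the protocol itself says that some of these patients may not perceive them. The pre-test check deals with lows present at the start. What remains is a new low that neither participant nor examiner notices.

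Two things are at stake. The first is safety: a participant enrolled because of ongoing hypoglycemia could leave the unit with an unrecognised low, and no glucose criterion for leaving is written. The second is interpretation: the study asks about the effect of recurrent hypoglycemia, and acute hypoglycemia also impairs cognition. Without a reading near the memory tasks, the study cannot say what glucose was when a low score was obtained, and this cannot be reconstructed later.

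**Working it through.** **Where glucose is checked (III.f)**

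| Point in the visit | Reading scheduled? | Action |
|---|---|---|
| Visit assessment (untimed, listed before the BDI) | Yes | None stated separately |
| Before cognitive testing | Yes | Treat below 70 mg/dL; recheck every 15 minutes until above 80 |
| During testing | Only if symptoms develop | As above; resume above 80 |
| Breaks | No | None |
| End of battery or departure | No | None |

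The length of the battery is not stated. It includes a 20-minute RAVLT delay, four other components and optional breaks. The documents do not say whether participants arrive fed or fasting, although the Background describes after-meal hypoglycemia as the commonest pattern. Section IV (Risks to Subjects) does not list hypoglycemia during the visit.

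**Size of the effect**

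The plan gives no figure to reproduce: there is no rate of silent lows, no acute effect and no power calculation. The inputs below are assumptions, except for 20 per group (III.c).

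- Share of a group with a silent low during the battery: 5 to 20%.
- Acute loss on the memory score: 0.5 to 1.0 SD.
- Share of these lows that overlap the memory tasks: 50 to 100%.

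Shift in the group mean = rate × overlap × loss.
- Smallest: 0.05 × 0.5 × 0.5 = 0.0125 SD.
- Largest: 0.20 × 1 × 1.0 = 0.20 SD.

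Standard error of a two-group difference = sqrt(2/20) = 0.316 SD. The shift is therefore 0.0125/0.316 = 0.04 to 0.20/0.316 = 0.63 standard errors.

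Rejection rate of a four-group one-way ANOVA, 20 per group, alpha 5%, no lasting effect of hypoglycemia, 200,000 simulated trials per cell:

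| Overlap | Groups affected | 5%, 0.5 SD | 10%, 1.0 SD | 20%, 0.5 SD | 20%, 1.0 SD |
|---|---|---|---|---|---|
| Full | One | 5.1% | 5.8% | 5.9% | 8.4% |
| Full | 1 and 3 | 5.1% | 6.0% | 6.1% | 9.6% |
| Half | One | 5.0% | 5.2% | 5.2% | 5.9% |
| Half | 1 and 3 | 5.1% | 5.2% | 5.3% | 6.1% |

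An independent repeat gave 5.0 to 6.2% everywhere except the extreme full-overlap scenario, where it gave 8.5% (one group) and 9.3% (Groups 1 and 3).

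**Safety**

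Chance of at least one silent low among the 40 participants of Groups 1 and 3 = 1 − (1 − p)^40. For assumed p of 1%, 5% and 10% this is 33%, 87% and 98.5%, with 0.4, 2 and 4 participants expected.

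**What normal readings would show**

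If none of those 40 had a low at a given check, the one-sided 95% upper bound on the rate at that check would be 1 − 0.05^(1/40) = 7.2%.

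**The case against.** The strongest reply is that this is a low-risk observational pilot whose size is set by feasibility. No drug, insulin, meal challenge or required fast is written, and testing takes place on a clinical research unit. A silent low at departure is then mainly the background risk these patients carry every day. Glucose is already checked and treated before testing. The symptom trigger is not limited to self-report, and an examiner might notice changes in thinking or attention. The statistical effect is close to nil in most scenarios.

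Much of this stands. It limits the weight of the point and rules out a claim of material bias. It does not close the gap: examiner observation is not written as a trigger, and a low without visible signs would still be missed. The protocol already judged glucose monitoring necessary at this visit, so extending it by two readings is a small step.

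Three stronger readings are tempting and are not supported. A reader might infer that silent lows could account for the group difference in memory; the documents give no rate, effect or overlap, and the rejection rate leaves the neighbourhood of 5% only when all three assumptions are at their extreme. A reader might infer that the treatment snack provokes a later reactive low; the documents do not say so, and it would concern only those below 70 mg/dL at the start. A reader might infer that silent lows in Group 2, defined only by absence of symptomatic hypoglycemia, mask a true difference; that is possible and no more.

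**Conclusion.** The point holds as a cheap improvement. On the text, symptoms are the only trigger for a glucose reading after testing starts, and no end-of-battery or departure check exists, in a study that warns of unawareness in the condition it enrols. That conclusion depends on no assumed rate.

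The bias is of unknown size and probably small: 0.0125 to 0.20 SD under the assumptions shown, most likely towards exaggerating a deficit in Groups 1 and 3. The reasons to act are safety and being able to describe glucose at testing.

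The added readings have limits. A reading after delayed recall cannot protect the memory score. It does not establish glucose during RAVLT learning or Letter-Number Sequencing, and single readings can miss a transient low. Zero lows in 40 would bound the rate at one moment only, and a bound of 7.2% would not exclude a rate of 5%. It should not be inferred that excluding participants with lows would separate acute from lasting effects.

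**What to change.** In III.f, for all four groups and regardless of symptoms, add two capillary readings and record value and clock time:

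1. At the first break after RAVLT delayed recall, never between learning and recall.
2. At the end of the battery, before departure. If delayed recall is the last task, this reading serves for both.

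If a reading is below 70 mg/dL, treat and recheck every 15 minutes until above 80 mg/dL before testing resumes or the participant leaves. The departure condition is a new criterion and should be written as one. An asymptomatic reading of 70 mg/dL or more needs no action; without that sentence, a participant at 70 to 80 mg/dL would be neither treated nor free to go on. Keep the existing symptom-triggered check.

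In III.h, report lows by group and keep the memory analysis in all participants as primary. Any analysis excluding participants below 70 mg/dL at the memory-adjacent reading should be labelled descriptive, because it may remove the most affected patients and rests on a single reading.

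Cost: protocol wording, two case report form entries, up to 2 × 80 = 160 extra fingersticks, and an occasional treatment pause of 15 minutes or more, likelier in Groups 1 and 3.
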